**Protocol Test Abstract:**

This study involves evaluating the accuracy of using Masimo’s INVSENSOR00026 Pulse CO-Oximeter and Sensor to measure hemoglobin, as compared to hemoglobin measurements obtained from various lab analyzer(s). The performance of the sensors will be calculated using arithmetic root mean square (ARMS) analysis of the SpHb values and the reference blood values. Blood samples will be collected from healthy volunteers who undergo a hemodilution procedure wherein blood is repeatedly sampled as the concentration of hemoglobin is reduced by administering intravenous fluids to the volunteer in a controlled manner.

**STATEMENT OF COMPLIANCE**

This document is a protocol for a clinical research study sponsored by Masimo Corporation. The study will be conducted in compliance with all stipulations of this protocol, the conditions of IRB approval, federal and local regulatory requirements, 21 CFR Part 50, 21 CFR Part 56, 21 CFR Part 812, ISO-14155, and International Conference on Harmonisation Good Clinical Practice (ICH GCP).

The protocol, informed consent form(s), recruitment materials, and all participant materials will be submitted to the Institutional Review Board (IRB) for review and approval. Approval of both the protocol and the consent form must be obtained before any participant is enrolled. Any amendment to the protocol will require review and approval by the IRB before the changes are implemented to the study. In addition, all changes to the consent form will be IRB-approved; a determination will be made regarding whether a new consent needs to be obtained from participants who provided consent, using a previously approved consent form.

**1. PURPOSE**

The primary objective of this clinical investigation is to evaluate the accuracy of using Masimo’s INVSENSOR00026 Pulse CO-Oximeter and Sensor to measure hemoglobin, as compared to hemoglobin measurements obtained from various lab analyzer(s). Data using the noninvasive devices will be collected from healthy volunteers undergoing a hemodilution procedure.

This is a nonrandomized single arm study wherein all subjects are enrolled into the experimental arm and receive the INVSENSOR00026 Pulse CO-Oximeter and sensor. Hemodilution will be conducted by delivery of intravenous fluids in a controlled manner to reduce the subject’s blood concentration of hemoglobin to obtain noninvasive hemoglobin readings SpHb at various levels. Reference blood samples will be repeatedly collected from the subject and analyzed using a standard laboratory hematology analyzer. The performance of the sensors will be calculated using arithmetic root mean square (ARMS) analysis of the SpHb values and the reference blood values.

Outcome Measure: Performance of INVSENSOR00026 by ARMS calculation

Performance of the Pulse CO-Oximeter and sensors will be determined by comparing the noninvasive hemoglobin measurement (SpHb) of INVSENSOR00026 to the hemoglobin value obtained from a reference blood sample and calculating the ARMS value.

**2. BACKGROUND**

Masimo Corporation develops non-invasive medical technologies. These devices have applications in the operating room, critical care unit, emergency room, emergency transport vehicles, as well as physician’s offices.

[figure not shown]
A blood sample gives the best measure of hemoglobin as well as other blood solutes but is difficult to measure continuously and without skin puncture and risk of infection. Masimo SET and Masimo Rainbow technology allows real-time, non-invasive monitoring of hemoglobin (and other blood solutes) in patients and has the potential to improve clinical outcomes while reducing the cost of care and risks to both patients and clinicians associated with venipuncture.

**2.1. TECHNOLOGY BACKGROUND**

Pulse oximetry is governed by the following principles:

- Oxyhemoglobin (oxygenated blood) and deoxyhemoglobin (non-oxygenated blood) differ in their absorption of red and infrared light (spectrophotometry).
- The amount of arterial blood in tissue changes with arterial pulses (photoplethysmography). Therefore, the amount of light absorbed by the varying quantities of arterial blood changes as well.

- More generally, Masimo Pulse CO-Oximeters use a multi-wavelength sensor to distinguish between not only oxygenated blood and deoxygenated blood, but also blood with carbon monoxide, oxidized blood and blood plasma. The CO-Oximeter utilizes a sensor with various light-emitting diodes (LEDs) that pass light through the site to a photodiode (detector). See figure below.

1. Light Emitting Diodes (LEDs) (2+ wavelengths)
2. Detector

- Signal data is obtained by passing various [REDACTED] lights through a capillary bed (for example, a fingertip, a hand, a foot) and measuring changes in light absorption during the blood pulsatile cycle. The detector receives the light, converts it into an electrical signal. Once the oximeter receives the signal from the sensor, it utilizes Masimo Rainbow signal extraction technology for calculation of the patient’s hemoglobin level.

2.2. STUDY DEVICES

Investigational sensor: INVSENSOR00026 (Pulse CO-Oximeter and sensor)

The devices used in this study are manufactured per Good Manufacturing Practice (GMP) with traceability of lot or serial numbers and will be labeled as investigational devices, for clinical research only. Final marketed names for the sensor and/or device may change.

The INVSENSOR00026 is a system composed of a handheld Pulse CO-Oximeter and sensor with Rainbow technology similar to already cleared Masimo noninvasive Pulse CO-Oximeters and sensor. The system is intended for spot-check measurements on patients in various care area settings (hospitals, hospital-type facilities, and clinics). The device is a more compact version of already 510(k) cleared Rad-57 and Pronto devices. The Pulse CO-Oximeter device also comes with an upgraded display with touchscreen capabilities. The INVSENSOR00026 Pulse CO-Oximeter and sensor are connected by an accessory patient cable.

The reusable INVSENSOR00026 sensor is intended to measure non-invasive physiological parameters such as SpO2, SpHb, PR, and PI, similar to the existing FDA cleared Masimo rainbow reusable sensors. The sensor has a slimmer and more compact design compared to other Masimo reusable finger sensors. The sensor is intended to be used on patients weighing greater than 3 kg.

**5. STUDY POPULATION**

**5.1. Inclusion Criteria**

- Subject is 18 - 50 years of age.
- Subject weighs a minimum of 110 lbs and no more than 250 lbs unless subject is over 6 feet tall.
- Hemoglobin value is greater than or equal to 11 g/dL at time of screening
- Baseline heart rate  $\geq 45$  bpm and  $\leq 85$  bpm.
- CO value  $\leq 2.0\%$  FCOHb
- Subject has a physical status of ASA I or II (American Society of Anesthesiology Class I; Healthy subjects without any systemic disease at all. American Society of Anesthesiology Class II; subjects with mild systemic disease) as it applies to the systemic disease portion of the classification.
- Systolic Blood Pressure  $\leq 140$  mmHg and Diastolic Blood Pressure  $\leq 90$  mmHg.
- Subject is able to read and communicate in English and understands the study and risks involved.

**5.2. Exclusion Criteria**

- Subject is pregnant
- Subject smokes (including e-cigarette use)
- Subject has a BMI  $> 35$  and has been classified as morbidly obese or at an increased risk for participation by a medical professional.
- Subject has a history of fainting (vasovagal), blacking out or losing consciousness during or after a blood draw.
- Subject has open wounds, inflamed tattoos or piercings, or any visible healing wounds.
- Subject has known drug or alcohol abuse or uses recreational drugs.

- Subject has experienced a head injury with loss of consciousness within the last year.
- Subject has taken anticoagulant medication within the last 30 days.
- Subject has any chronic bleeding disorders (i.e. hemophilia).
- Subject has any history of a stroke, myocardial infarction, heart attack, or seizures.
- Subject has any cancer or history of cancer (not including skin cancer).
- Subject has a chronic neurological disease (i.e. multiple sclerosis, Huntington's disease).
- Subject has any cardiac dysrhythmias (i.e. atrial fibrillation) and has not received clearance from their physician.
- Subject has known neurological and/or psychiatric disorder (i.e. schizophrenia, bipolar disorder) that interferes with the subject's level of consciousness.
- Subject has Wolff-Parkinson-White Syndrome or Stokes-Adams Syndrome
- Subject has any medical condition which in the judgment of the investigator and/or medical staff, renders them ineligible for participation in this study (Discretion of investigator).
- Subject has taken opioid pain medication within 24 hours of start of study.
- Subject has any type of infectious disease (i.e. Hepatitis, HIV, Tuberculosis, Flu, Malaria, Measles, etc.).
- Subject is taking medications known to treat any type of infectious disease.
- Subject has either signs or history of peripheral ischemia or carpal tunnel.
- Subject has had invasive surgery within the past year- including but not limited to major dental surgery, gallbladder, heart, appendix, major fracture repairs (involving plates/ screws), jaw surgery, Urinary tract surgery, plastic surgery, major ENT surgery, joint replacement or gynecological surgeries, heart surgery or thoracic surgery.
- Subject has symptoms of congestion, head colds, flu, or other illnesses
- Subject has donated blood within the last 2 weeks.
- Subject is claustrophobic or has generalized anxiety disorder.
- Subject has been in severe car accident(s) or a similar type of accident(s) requiring hospitalization within the last 12 months.
- Subject has had a concussion within the last 12 months.
- Subject has chronic unresolved asthma, lung disease or respiratory disease.
- Subject is allergic to lidocaine, latex, adhesives, or plastic.
- Subject has heart conditions, insulin-dependent diabetes or uncontrolled hypertension.
- Subject has delivered vaginally, has had a pregnancy terminated, a miscarriage with hospitalization, or had a C-section within the last 6 months.
- Subject intends on participating in any heavy lifting, repetitive movement of their wrist (including riding a motorcycle) or exercise (working out, riding a bike, riding a skate board etc.), or any activity that will put additional stress on the wrist within 24 hours following a study that involves an arterial line.
- Discretion of investigator/study staff

### 5.3. **Withdrawal of subjects**

Subjects must be withdrawn under the following circumstances:

- 5.3.1. The subject withdraws consent.
- 5.3.2. Discretion of investigator, for example: the investigator feels that the subject is too money motivated, the investigator feels that the subject does not fully comprehend and understand the consent form, the subject is ill-mannered and/or shows aggressive behavior towards study staff,

malfunction of the device for greater than 30 minutes that prevents accurate collection of optical data.

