5.4. Replacement of subjects

In case a subject is withdrawn from the study, another subject may be recruited.

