**8. ACCEPTANCE CRITERIA (JUSTIFY IF NOT APPLICABLE)**

The pulse co-oximeter and sensors will be determined to have equivalent performance based on the agreement of their ARMS values.

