9.2. Statistical Analysis

Accuracy will be reported as the root mean squared error (ARMS) of the SpHb-tHb parameter. Per ISO 80601 Part 2-61, accuracy of existing pulse oximetry instruments will be reported using ARMS standard calculations which are also applicable to SpHb testing.

$$Bias = \frac{1}{n} \sum_{i=1}^n (SpHb - tHb)$$

$$A_{RMS} = \sqrt{\frac{\sum_{i=1}^n (SpHb - tHb)^2}{n}}$$

9.3. Measures taken to minimize/avoid bias:

- 9.3.1. Sensors and devices will be provided to operators in a way that minimizes the operator bias. Sensors and devices will be provided at random when deemed necessary.
- 9.3.2. Operators will not make any decisions based on results from other operators or any parameters obtained from blood samples.

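### Does withdrawing and replacing subjects after a device malfunction make the reported ARMS too favourable?

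*Combined protocol and SAP*

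**What the plan says.** Section 5.3 opens with "Subjects must be withdrawn under the following circumstances". Item 5.3.2 begins "Discretion of investigator, for example: the investigator feels that the subject is too money motivated" and ends its list of examples with "malfunction of the device for greater than 30 minutes that prevents accurate collection of optical data". On replacement, section 5.4 says: "In case a subject is withdrawn from the study, another subject may be recruited".

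Section 1 names a single outcome: "Outcome Measure: Performance of INVSENSOR00026 by ARMS calculation". Section 9.2 states: "Accuracy will be reported as the root mean squared error (ARMS) of the SpHb-tHb parameter". It gives formulas for Bias and ARMS that sum the SpHb-tHb differences from i = 1 to n. It names no analysis set, no criterion for an evaluable pair and no exclusion rule. Section 8 says that the pulse co-oximeter and sensors "will be determined to have equivalent performance based on the agreement of their ARMS values", with no numeric limit.

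Section 10 counts malfunctions among device deficiencies, but 10.1 to 10.3 give recording and reporting rules only for adverse events, serious adverse events, unanticipated device effects and unanticipated problems. Section 12.2 has device and sensor use recorded on each subject's case report form, section 15 calls for a separate monitoring plan, and section 16 has deviations documented.

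**The concern.** A withdrawal trigger that depends on the performance of the device under test deserves attention in an accuracy study. If subjects in whom the device fails are removed, replaced and left out of ARMS, the result describes the device only when it works. With ARMS as the sole outcome and the basis for acceptance, no second measure would reveal the loss. The public text plans no count of malfunctions or of blood draws without a valid SpHb, so a reader of the result could not judge how much had gone. If the lost pairs had larger errors than the kept ones, the reported ARMS would be optimistic.

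Three details seem to add to this. The mandatory lead-in of 5.3 sits above an item headed as discretion. The malfunction clause does not say which device it means, although the schedule in 7.1 lists both test and control sensors. And 9.3.2 restricts operators, while 5.3.2 leaves withdrawal to the investigator.

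**Working it through.** The plan gives no figure to reproduce: the sample size is redacted, and no ARMS limit, malfunction rate or error SD is visible. The check is first a reading of the text, then an illustration.

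**What the text does to a pair**

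1. Section 5.3 removes a subject from further participation. It says nothing about discarding data already collected.
2. Section 5.4 permits a further subject to be recruited. It does not say that the new subject's pairs take the place of the earlier subject's.
3. Section 9.2 sums over all n pairs. With no exclusion stated, the plain reading is that n counts every SpHb-tHb pair obtained.
4. During a malfunction that meets the clause there is usually no usable SpHb, hence no pair and no contribution to ARMS under any convention.

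The only pairs at issue are those obtained before the malfunction, or degraded ones around it.

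**What would happen if pairs were dropped all the same**

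Let f be the share of obtained pairs dropped, and r the ARMS in dropped pairs divided by the ARMS in kept pairs. Both are assumptions; the documents give neither. Because ARMS squared is a mean of squared differences,

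ARMS(all)² = (1 - f) × ARMS(kept)² + f × ARMS(dropped)²

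and so

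reported / all-pairs = 1 / √(1 - f + f r²).

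| f | r | √(1 - f + f r²) | Change in reported ARMS |
|---|---|---|---|
| 0 (pairs kept, or no reading) | any | 1 | 0% |
| any | 1 | 1 | 0% |
| 2% | 0.5 | √0.985 = 0.9925 | +0.8% |
| 2% | 2 | √1.06 = 1.0296 | -2.9% |
| 5% | 0.5 | √0.9625 = 0.9811 | +1.9% |
| 5% | 1.5 | √1.0625 = 1.0308 | -3.0% |
| 5% | 2 | √1.15 = 1.0724 | -6.7% |
| 10% | 0.5 | √0.925 = 0.9618 | +4.0% |
| 10% | 1.5 | √1.125 = 1.0607 | -5.7% |
| 10% | 2 | √1.30 = 1.1402 | -12.3% |

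A negative sign means that the reported ARMS is too favourable. The range crosses zero, and its largest value is simply the corner of the chosen grid. Under the formula as written, f = 0 and the first row applies.

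**The three details**

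- The lead-in and the discretion item read together: once the investigator has decided, the subject is withdrawn.
- Section 6 lists one test device and the clause concerns optical data, so the test device is the natural reading.
- Section 9.3.2 says "Operators will not make any decisions based on results from other operators or any parameters obtained from blood samples". Withdrawal for malfunction rests on how long the device fails and on loss of optical data, not on the SpHb-tHb difference. Different roles are governed by different rules, and nothing conflicts.

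**The case for a change.** The best case for a change is that the text leaves a choice open. One analyst could keep a withdrawn subject's earlier pairs and another could drop them, and no sentence in 9.2 would settle which is right. That choice could be made after the errors are known, and it concerns the only outcome. Section 2.2 describes a spot-check system, so how often it fails to give a reading is useful performance information beside accuracy. A clarification would need no extra subjects or blood draws. Beyond the grid above the effect could also be larger: with f = 20% and r = 3, both assumed, the all-pairs ARMS would be √(0.8 + 0.2 × 9) = 1.61 times the reported one.

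Some of this stands. The analysis set is not written down, 10.1 to 10.3 set no recording rule for a malfunction that harms nobody, and no malfunction or no-reading count is planned in the public text. But the two analysts are not on an equal footing: one applies the formula as printed, the other adds an exclusion. Nothing in the documents suggests that pairs taken before a malfunction are less accurate. A no-reading rate would be a second measure in a study whose stated objective is accuracy. The per-subject device record in 12.2 and the deviation record in section 16 do not promise a malfunction table, but they are places where a malfunction can be noted. Parts of 7.4 and 9.4 are redacted and may hold relevant handling, so silence there cannot be held against the plan.

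**Conclusion.** The concern does not hold as a fault in the plan. ARMS computed as section 9.2 states it, over all pairs obtained, is not altered by withdrawal or replacement after a malfunction. An effect requires an exclusion rule found nowhere in the public text; its direction is unknown, and its size rests wholly on assumed inputs (+4.0% to -12.3% for f of 2% to 10% and r of 0.5 to 2). With no numeric limit visible in section 8, no changed decision can be shown. What remains is an unwritten definition of n, which a competent analyst fills by keeping every valid pair and accounting for withdrawn and replaced subjects when reporting. This rests on reading n as all pairs obtained, and on the redacted text containing no contrary rule.

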5.4. Replacement of subjects

In case a subject is withdrawn from the study, another subject may be recruited.

6. EQUIPMENT AND MATERIALS

Equipment and Materials: All lab analyzers and equipment will be maintained per manufacturer specifications and all study personnel will be trained on the use of relevant equipment. Equivalent equipment and materials to those listed below may be used.

Safety Equipment (FDA-Cleared)

- Blood pressure monitoring system
- A-line pressure transducer
- Electrocardiogram (ECG)
- Masimo Pulse Oximeters (Radical-7) - for subject safety monitoring
- Pulse oximeter sensors and cables (Masimo SET, Masimo rainbow)
- Masimo Patient Monitoring Platform (Root®)- for subject safety monitoring
- Medical-grade Oxygen tank and mask
- Crash cart

Test Devices

- Masimo INVSENSOR00026 pulse co-oximeter and sensor – Investigational

Research Equipment

- Laboratory co-oximeters/blood analyzers
- Laboratory hematology analyzers

7. PROCEDURE

7.1. SCHEDULE OF ACTIVITIES

Procedures	Phone Pre-Screen	Baseline Visit 1	Procedure Visit 1
Brief Study Procedure Description	X		
Informed consent		X	
Demographics (including skin tone)	X	X	
Medical history (subject-reported)	X	X	
Concomitant medication review	X	X	
Vital Signs (ECG, Blood Pressure Cuff, Pulse Ox)		X	X
Height	X	X	
Weight	X	X	
ASA Status Assessment		X	
Pregnancy test 		X	
Allen’s Test		X	
Venous sample (via needle stick or IV placement)		X	

Procedures	Phone Pre-Screen	Baseline Visit 1	Procedure Visit 1
Local anesthetics (lidocaine, ethyl chloride spray, or pain ease skin refrigerant) as needed 		X	X
Peripheral Venous Line (IV) 		X	X
Intra-arterial catheter (A-line)			X
Placement of test and control sensors			X
Noninvasive data collection			X
Removal of Blood (if necessary)			X
IV Fluid Administration			X
Continuous A-line sampling			X
Line Removal			X
Post Care Instructions Given		X	X
Discharge		X	X
Adverse Event Review and Evaluation 		X	X

1 hCG (urine) pregnancy test (all female subjects)

2 IV may be placed during screening/baseline to obtain qualifying venous sample at discretion of medical staff. If the IV is placed during screening/baseline, medical staff will offer to use local anesthetics.

3 Adverse events may be reported by the subject after their visit. See section 10 for additional details.

**7.2. RECRUITMENT AND PRESCREENING**

Subjects will be recruited using IRB-approved advertisements. Subjects may be referred to the study by previous volunteers. Subjects are contacted via phone call to conduct a prescreening interview to determine their initial eligibility for the study. Potential eligible subjects are scheduled for a study visit to the clinical laboratory.

**7.3. CONSENTING AND SCREENING**

- 7.3.1. Study staff will discuss the informed consent process and the study with the potential subjects. The subjects will be provided with enough time to read and understand the informed consent document and their questions will be answered by study staff prior to the subject signing the informed consent form. No study related activities will be conducted until consent is signed. If the subject fails to provide proper documentation on their individual consent form for any study, Masimo has the right to re-contact the subject and ask them to return to the clinical lab in order to properly complete the consent form or subject bill of rights.
- 7.3.2. The subject’s weight and height are self-reported, however if the subject appears to be outside the weight range based on the inclusion/exclusion criteria, the subject will be weighed on a scale for verification.
- 7.3.3. Subjects will be asked to provide a copy of their valid government photo ID and/or Social Security card (SSN) to verify subject identity. The copies of these forms of identification will be stored along with the subject’s consent. The confidentiality and retention of these documents will be protected to the extent provided and required by law.
- 7.3.4. Subjects will be asked a brief series of health questions to ensure their eligibility for this study. Subjects who do not meet the inclusion and exclusion criteria will not be eligible to participate in the study.

- 7.3.5. Subject demographic information including age, sex, skin tone, ethnicity, height and weight will be collected. These may be recorded for data analysis and/or subject safety monitoring purposes.
  - 7.3.6. In addition, a medical history will be recorded after the initial screening questionnaire.
  - 7.3.7. Pre-procedure vital signs will be recorded for subject safety monitoring. Spikes in blood pressure and heart rate can be expected during line placement, needle sticks, blood draws etc. and may also be attributed to anxiety/nervousness relating to a new environment. Only the initial recorded blood pressure and/or heart rate determines a subject’s qualification for the study.
  - 7.3.8. Female subjects will be required to take a pregnancy test. Results will be noted in study documentation. If the pregnancy test is positive, the subject will be notified and removed from the study.
  - 7.3.9. A venous sample will be obtained via needle stick or by placement of an IV and analyzed to verify that the subject meets the inclusion criteria for hemoglobin level. The subject will be excluded from the study if the values from the blood draw fall outside the ranges stated in the inclusion criteria.
  - 7.3.10. Subjects may have a blanket placed on them or hot water bottles placed under their hands.
  - 7.3.11. Subjects may be offered a snack (e.g., granola bar) and/or beverage (e.g., water, juice) due to the amount of time their involvement in this study may take.
- 7.4. **PROCEDURES**
- 7.4.1. Standard hospital-type monitors will be placed on the subject, including ECG and blood pressure, for safety monitoring by medical staff. The procedure will be stopped if there is any evidence of volunteer stress or distress. These signs include but are not limited to a rise or fall in mean arterial blood pressure of more than 30% from baseline, a rise in heart rate to more than 130 BPM, complaints of feeling faint, chest discomfort, GI distress, urinary discomfort or feelings of a bloated bladder, or alternation of mental status. Blood samples are also monitored for hemoglobin and/or blood oxygenation levels for subject safety.
  - 7.4.2. A peripheral venous line will be placed in the volunteer’s hand or arm. One or more venous sampling catheters will be used during the study for the removal of blood and administration of fluids.
  - 7.4.3. Local anesthetics such as lidocaine, ethyl chloride spray, or Pain Ease skin refrigerant spray may be used in the event that an IV is placed to numb the site. Subjects will be given the option to have lidocaine or numbing spray be used during IV placement for the purpose of making catheter placement more comfortable for the subjects.
  - 7.4.4. After intravenous access is established, one or more intra-arterial catheter(s) (arterial line or A-line) will be placed in the radial artery of the volunteer’s wrist. The A-line is placed to facilitate continuous blood pressure measurement for subject safety monitoring, to enable repeated removal of blood aliquots for reference hemoglobin values, [REDACTED]
  - 7.4.5. After arterial access is established, optical sensors for the noninvasive measurement(s) will be placed on the subject’s fingers.

- 7.4.6. Upon successful placement of the sensors and the volunteer’s indication that they are comfortable, a baseline set of blood samples will be obtained.
- 7.4.7. [REDACTED]
- 7.4.8. Following removal of blood, the volunteer will rapidly receive intravenous fluid [REDACTED]
- 7.4.9. [REDACTED]
- 7.4.10. [REDACTED] blood samples [REDACTED] will be drawn at selected time intervals throughout the study while intravenous fluid is being administered for laboratory analysis of hemoglobin concentration. [REDACTED]
- 7.4.11. The total amount of blood removed from the subject may be up to [REDACTED]
- 7.4.12. [REDACTED]
- 7.4.13. The hemodilution procedure will continue until the subject’s fluid limits have been reached [REDACTED] or the target hemoglobin value has been reached.
- 7.4.14. At the conclusion of the procedure, the sensors/devices, IV(s) and the arterial line(s) will be removed and the volunteer will be allowed to leave after medical personnel determine it is safe to do so.
- 7.4.15. At the end of the hemodilution procedure, if the last arterial blood draw hemoglobin value is below 8.0 g/dL, then the subject’s hemoglobin level will be monitored using an FDA cleared pulse oximeter. Subjects who have a hemoglobin level below 8.0 g/dL must remain in the study area for observation and meet a minimum rise in hemoglobin of 0.5 g/dL prior to leaving the study area, or until medical staff determines it is safe to do so. If medical staff finds it is not safe to do so, the subject will be referred to an urgent care facility.
- 7.4.16. All volunteers will be encouraged to remain in the study area until they feel fit to leave. Subjects should feel safe and able before returning to work directly after participation in the study. Subjects who are employees of Masimo will be advised to take as much time as they need after the study before returning to work.
- 7.4.17. Volunteers will be given instructions on wound care. All volunteers will be instructed to contact the principal investigator in the event of any potential complication.
- 7.4.18. The total time for the study procedures will be up to [REDACTED]. [REDACTED]. Volunteers will be paid according to the compensation breakdown on the consent form.

- 7.4.19. Subjects will be provided with information related to any significant new findings that develop at any time during the study which may relate to their willingness to continue their participation, their health and/or medical care.
- 7.4.1 After the study has ended subjects will be offered a snack (eg. Granola bar) and something to drink (eg. water or juice). Subjects are asked to consume food and/or liquid prior to leaving the clinical lab area for their safety due to study procedures such as blood removal and line placement. Subjects may also be asked to wait in the clinical lab or lobby waiting area for an additional 30 minutes (estimate) before leaving to allow for their body to continue adjusting after the study has completed.

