**9. SAMPLE SIZE JUSTIFICATION AND DATA ANALYSIS PROCEDURE TO BE USED**

9.1. Sample size determination

Sample size for this study has been determined to be [REDACTED] based on previous experience with similar devices and Masimo internal procedures for sample size calculation and justification ([REDACTED]).

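### Weight and height are self-reported and height is never verified, so the weight criterion, its 6-foot waiver and the numeric part of the BMI exclusion can be applied to wrong values

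*Combined protocol and SAP*

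**What the plan says.** Two eligibility rules use body size. Section 5.1 requires: "Subject weighs a minimum of 110 lbs and no more than 250 lbs unless subject is over 6 feet tall". Section 5.2 has a joint exclusion. BMI must be above 35, and the subject must also meet the second half of the sentence: "and has been classified as morbidly obese or at an increased risk for participation by a medical professional".

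Section 7.3.2 gives the method: "weight and height are self-reported, however if the subject appears to be outside the weight range". Only for such a subject does it add that "the subject will be weighed on a scale for verification". It has no corresponding step for height.

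Section 7.3.5 says: "Subject demographic information including age, sex, skin tone, ethnicity, height and weight will be collected". It continues: "These may be recorded for data analysis and/or subject safety monitoring purposes". The schedule in Section 7.1 marks height and weight at the phone pre-screen and at Baseline Visit 1 but gives no method for either, so it does not override 7.3.2.

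**The concern.** A limit on weight or height protects a volunteer only if it is applied to a value close to the true one. Height matters most here. Being over 6 feet is enough on its own to remove the 250 lb limit, and height enters BMI as a square, yet it is the one value with no verification step at all.

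Other entry criteria are checked on site: hemoglobin by venous sample (7.3.9), pregnancy by test (7.3.8), blood pressure and heart rate by recorded vital signs (7.3.7). Body size is treated differently, and no reason is given.

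At stake is whether the protocol's own entry limits are met in healthy volunteers who have no direct benefit (13.1) and undergo a procedure with the risks listed in 13.7. Section 7.3.5 also allows the same values to be used for data analysis or safety monitoring, so an error may not stop at eligibility.

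**Working it through.** The plan states no figure to reproduce on this point. The check reads 5.1, 5.2, 7.1 and 7.3 together and then asks what the weighing trigger can and cannot catch.

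**Inputs from the documents:** weight range 110 to 250 lb, with the upper limit waived above 6 ft, i.e. 72 in (5.1); BMI cut-off 35 (5.2); weighing triggered by the weight range only (7.3.2).

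**Formula:** BMI = (lb × 0.45359) / (in × 0.0254)².

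**1. The height waiver.** Assume a subject truthfully reports 260 lb, and reports 6 ft 1 in (73 in) when true height is 5 ft 11 in (71 in).
- As reported: 117.9 kg / (1.854 m)² = 34.3. Height is over 72 in, so the 250 lb limit is waived.
- True: 117.9 kg / (1.803 m)² = 36.3. Height is not over 72 in, so the 250 lb limit applies and the subject fails 5.1.

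Weighing this subject would only confirm 260 lb. The deciding value is height, which is not checked.

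**2. Does the weighing trigger cover BMI?** Set 250 lb equal to BMI 35: height = √(113.4 / 35) = 1.800 m = 70.9 in. Below that height a subject can exceed BMI 35 without leaving the weight range:

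| Height (in) | Weight at BMI 35 (lb) | BMI at 250 lb |
|---|---|---|
| 64 | 203.9 | 42.9 |
| 66 | 216.8 | 40.4 |
| 68 | 230.2 | 38.0 |
| 70 | 243.9 | 35.9 |

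A 64 in subject anywhere from 204 to 250 lb has a BMI of 35.0 to 42.9 and does not meet the trigger for being weighed.

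**3. How small an error crosses BMI 35?** Take a reported BMI of 34.0 at heights of 64 to 70 in, i.e. reported weights of 198.1 to 237.0 lb. The reporting errors are assumptions; the documents give none.

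| Assumed misreport | True BMI across 64 to 70 in |
|---|---|
| Weight 5 lb too low | 34.7 to 34.9 |
| Weight 5 lb too low and height 0.5 in too high | 35.2 to 35.4 |
| Weight 10 lb too low | 35.4 to 35.7 |

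In the last row the true weight is at most 237.0 + 10 = 247.0 lb, still inside the range.

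**4. The lower limit.** A subject of 104 lb who reports 112 lb passes the 110 lb floor on an 8 lb error. Whether anyone is weighed depends on a judgment of appearance with no stated tolerance.

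**The case against.** The strongest reply is that self-report is an openly stated choice, contradicts nothing else in the protocol, and is backed by other safeguards. These are ASA assessment, on-site vital signs, measured hemoglobin, investigator discretion to exclude, the stopping signs in 7.4.1, and a physician in attendance. That stands as far as it goes: these measures limit the consequences of a misreport. None of them establishes whether a subject meets the stated weight, height or BMI limits.

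Further points have force:

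- Section 7.3.2 does not confine the word *appears* to looks. A reported 260 lb could itself prompt a weighing. That narrows the gap for weight and leaves it open for height.
- The 250 lb limit is not an absolute ceiling. Section 5.1 lifts it above 6 feet and sets no other maximum, so a subject wrongly admitted at 260 lb is an undetected eligibility failure, not someone shown to be unsafe.
- The documents give no misreporting rate. The examples sit near the thresholds and show possibility, not frequency.

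Two stronger readings are tempting and are not supported. A reader might infer that a true BMI above 35 is enough to exclude a subject; Section 5.2 also requires the medical professional's classification. A reader might also infer that a misreported weight leads to wrong fluid or blood-removal volumes. Section 7.4.13 does continue the procedure until the subject's "fluid limits have been reached", but the basis of those limits is redacted and nothing visible ties them to body weight.

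**Conclusion.** The point holds as a weakness in eligibility verification. Height is never verified, and weight is verified only on a discretionary trigger. The weight criterion and its waiver can therefore be decided on wrong values, as can the numeric half of the BMI exclusion. A 2 in over-report of height is enough to reverse the weight criterion at 260 lb. Near the BMI cut-off, an under-report of 10 lb, or of 5 lb combined with half an inch of height, crosses 35 without the subject leaving the weight range.

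These sizes rest on assumed reporting errors and on reading 7.3.2 as the whole method, which the visible text supports. How many subjects would be affected cannot be estimated. The point does not touch the ARMS formula in 9.2, and it does not depend on the redacted sample size in 9.1. It is a modest point, worth acting on because the remedy is cheap.

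**What to change.** Change 7.3.2 so that every subject's weight and height are measured on site at Baseline Visit 1, and note in the 7.1 schedule that the baseline entries are measured and the phone pre-screen entries are reported. Compute BMI from the measured values, and apply the existing weight, 6-foot and BMI criteria to them. No threshold needs to change.

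The visit and both schedule items already exist, and 7.3.2 already assumes a scale. Section 6 lists neither a scale nor a height gauge, so both could be added there. The expected cost is minutes per subject (an estimate, not a figure from the documents) and possibly a few more screen failures, a category that 9.4 already anticipates.
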